10.2. Schedule of Time and Events

Table 2: Schedule of Events – Screening, Baseline, Double-Blind Treatment Period

| Study Procedure | Scre | ening | Baseline | | | | Ι | Double | -Blind | Treatr | nent P | eriod | | | | |
|--|------------------|-------------------|---------------------|-----|---|-----|-----------|-----------|--------|--------|----------|-------|----------|-----|-----|-----|
| | | | Study D Pretreat | 0 | Study Drug Concomitant Treatment AR101 Up-Dosing | | | | | | | | | | | |
| Visit (V) | V1 ¹² | V1a ¹³ | V2 | V3 | V4 | V5 | V6 | V7 | V8 | V9 | V10 | V11 | V12 | V13 | V14 | V15 |
| Week (W) ¹⁴ | -113 | before | D1 | W2 | W4 | W6 | W8 | W10 | W12 | W14 | W16 | W18 | W20 | W22 | W24 | W26 |
| Day (D) ¹⁴ | to -17 | -15 | 1 | 15 | 29 | 43 | 57 | 71 | 85 | 99 | 113 | 127 | 141 | 155 | 169 | 183 |
| Visit Window (d) | | | | ±3d | ±3d | ±3d | ±2d | ±2d | ±2d | ±2d | ±2d | ±2d | ±2d | ±2d | ±2d | ±2d |
| Screening/Baseline: | | | | | | | | | | | | | | | | |
| Informed Consent/Assent | Х | | | | | | | | | | | | | | | |
| ICF for optional assessments | Х | | | | | | | | | | | | | | | |
| Inclusion/Exclusion | Х | | Х | | | | | | | | | | | | | |
| Medical History/ | Х | | | | | | | | | | | | | | | |
| Demographics | | | | | | | | | | | | | | | | |
| Randomization | | | Х | | | | | | | | | | | | | |
| Training on Daily | | | | | Х | | | | | | | | | | | |
| Allergy Symptom Diary | | | | | | | | | | | | | | | | |
| Training on Study Drug Administration | | Х | Х | Х | | | | | | | | | | | | |
| Treatment: | | | | | | • | 1 | | | |   | |   | | | |
| Blinded Study Drug | | | Х | Х | Х | X | Х | Х | Х | Х | X | X | X | X | X | Х |
| SC Q2W | | | | | | | | | | | | | | | | |
| Administration ¹ | | | | | | | | | | | | | | | | |
| Subject Study Drug | | | Х | Х | Х | Х | Х | Х | Х | Х | X | Х | X | Х | Х | Х |
| Injection Log ¹ | | | | | | | | | | | | | | | | |
| AR101 Daily | | | | | Х | Х | Х | Х | Х | Х | Х | Х | Х | Х | Х | Х |
| Administration ² | | | | | IDED | | | | | | | | | | | |
| Daily subject AR101 | | | | | Х | Х | Х | Х | Х | Х | Х | Х | Х | Х | Х | Х |
| Dosing Diary ² | | | | | | | | | | | | | | | | |
| AR101 | | | | | X | Х | Х | Х | Х | Х | Х | Х | Х | Х | Х | Х |
| Dispensation/Account ³ | | | | | | | | | | | | | | | | j |

CONFIDENTIAL

Page 66 of 86

| Study Procedure | Scre | ening | Baseline | | | | Ι | Double | -Blind | Treatr | nent P | eriod | | | | |
|--|------------------|-------------------|---------------------|-----|-----|-----|-----|--------|--------|--------|--------|-------|-----|-----|-----|-----|
| | | | Study D Pretreat | | | | | | | | | | | | | |
| Visit (V) | V1 ¹² | V1a ¹³ | V2 | V3 | V4 | V5 | V6 | V7 | V8 | V9 | V10 | V11 | V12 | V13 | V14 | V15 |
| Week (W) ¹⁴ | -113 | before | D1 | W2 | W4 | W6 | W8 | W10 | W12 | W14 | W16 | W18 | W20 | W22 | W24 | W26 |
| Day (D) ¹⁴ | to -17 | -15 | 1 | 15 | 29 | 43 | 57 | 71 | 85 | 99 | 113 | 127 | 141 | 155 | 169 | 183 |
| Visit Window (d) | | | | ±3d | ±3d | ±3d | ±2d | ±2d | ±2d | ±2d | ±2d | ±2d | ±2d | ±2d | ±2d | ±2d |
| Epinephrine | | Х | Х | Х | Х | | | | | | | | | | | |
| Autoinjector Training | | | | | | | | | | | | | | | | |
| Con Meds/Procedures | Х | Х | Х | Х | Х | X | Х | Х | Х | Х | Х | Х | Х | Х | Х | Х |
| Efficacy ⁴ : | | | | | | | | | | | | | | | | |
| DBPCFC ⁵ | | Х | | | | | | | | | | | | | | |
| Peanut Skin Prick Test (SPT) ⁶ | Х | | | | | | | | | | | | | | | |
| Peanut SPT titrated ⁶ | | | Х | | Х | | | | | | | | | | | |
| EASI for AD, ACQ-5 | | Х | Х | Х | Х | Х | Х | Х | Х | Х | Х | Х | Х | Х | Х | Х |
| asthma | | | | | | | | | | | | | | | | |
| Daily Allergy | | | | | Х | Х | Х | Х | Х | Х | Х | Х | Х | Х | Х | Х |
| Symptom Diary ⁷ | | | | | | | | | | | | | | | | |
| FAQL Questionnaire | | | Х | | | | | | | | | | | | | |
| Safety ⁴ : | | | | | | | | | - | | - | | | - | | |
| Weight | Х | | Х | Х | Х | Х | Х | Х | Х | Х | Х | Х | Х | Х | Х | Х |
| Height | Х | | | | | | | | | | | | | | | |
| Vital Signs ⁸ | Х | Х | Х | Х | Х | Х | Х | Х | Х | Х | Х | Х | Х | Х | Х | Х |
| Physical Examination | Х | Х | | | | | | | | | | | | | | |
| Spirometry/Peak Flow ^{9, 9.a} | Х | Х | Х | Х | Х | X | Х | Х | Х | Х | Х | Х | Х | Х | Х | X |
| Adverse Events | Х | Х | Х | Х | Х | X | Х | Х | Х | Х | Х | Х | Х | Х | X | X |
| Laboratory Testing ⁴ : | | | | | | | | | | | | | | | | |
| HIV ab, HBsAg, | Х | | | | | | | | | | | | | | | |
| HBcAb, Hep C Ab | | | | | | | | | | | | | | | | |
| Hematology, Chemistry | Х | | Х | | Х | | | | Х | | | | Х | | | |
| FeNO Test ^{9, 9a} | | Х | Х | | Х | | Х | | Х | | Х | | Х | | Х | |
| Urinalysis | Х | | Х | | X | | 1 | | Х | | | Х | Х | Х | | X |

CONFIDENTIAL

Page 67 of 86

| Study Procedure | Scre | ening | Baseline | | | | Ι | Double | -Blind | Treatn | nent P | eriod | | | | |
|---|------------------|-------------------|---------------------|-----|---|-----|-----|-----------|-----------|--------|--------|-------|-----|-----|-----|-----|
| | | | Study E Pretreat | | Study Drug Concomitant Treatment AR101 Up-Dosing | | | | | | | | | | | |
| Visit (V) | V1 ¹² | V1a ¹³ | V2 | V3 | V4 | V5 | V6 | V7 | V8 | V9 | V10 | V11 | V12 | V13 | V14 | V15 |
| Week (W) ¹⁴ | -113 | before | D1 | W2 | W4 | W6 | W8 | W10 | W12 | W14 | W16 | W18 | W20 | W22 | W24 | W26 |
| Day (D) ¹⁴ | to -17 | -15 | 1 | 15 | 29 | 43 | 57 | 71 | 85 | 99 | 113 | 127 | 141 | 155 | 169 | 183 |
| Visit Window (d) | | | | ±3d | ±3d | ±3d | ±2d | ±2d | ±2d | ±2d | ±2d | ±2d | ±2d | ±2d | ±2d | ±2d |
| Pregnancy Test (WOCBP only) | S | | U | U | U | U | U | U | U | U | U | U | U | U | U | U |
| Total IgE | Х | | Х | | Х | | | | Х | | | | Х | | | |
| sIgE, sIgG4, sIgG Against Peanut Extract and Peanut Allergen Components | X | | Х | | X | | | | Х | | | | X | | | |
| Future Biomedical Research Sample (Optional) | | | Х | | Х | | | | Х | | | | Х | | Х | |
| Optional blood samples for additional exploratory research (eg, TruCulture, Basophil sensitivity, PBMC, allergen- specific T-cell profiling) ¹⁰ | | | X | | X | | | | | | | | | | | |
| DNA sample (Optional) ¹¹ | | | Х | | | | | | | | | | | | | |
| PK/Drug Concentratio | on and A | DA Samp | | | | _ | | | | | | | - | - | | |
| Functional dupilumab PK sample | | | Х | Х | | | X | | X | | Х | | Х | | Х | |
| Anti-dupilumab antibody sample | | | Х | | | | | | | | Х | | | | | |

 antibody sample
 antibody sample

 Abbreviations: S, serum; U, urine; FAQL, Food Allergy Quality of Life; FeNO, fractional exhaled nitric oxide; WOCBP, women of child bearing potential; PBMC, peripheral blood mononuclear cell; PK, pharmacokinetic

| Study Procedure | Double-Blind Treatment Period | | | | | | | | | | | |
|--|-------------------------------|------|------|--|------|------|--|--|--|--|--|--|
| | | S | | omitant Treatmen ng (if applicable) | ıt | | | | | | | |
| Visit (V) | V15a | V15b | V15c | V15d | V15e | V15f | | | | | | |
| Week (W) ¹⁴ | W28 | W30 | W32 | W34 | W36 | W38 | | | | | | |
| Day (D) ¹⁴ | 197 | 211 | 225 | 239 | 253 | 267 | | | | | | |
| Visit Window (d) | ±2d | ±2d | ±2d | ±2d | ±2d | ±2d | | | | | | |
| Screening/Baseline: | | | | | | | | | | | | |
| Informed Consent/Assent | | | | | | | | | | | | |
| ICF for optional assessments | | | | | | | | | | | | |
| Inclusion/Exclusion | | | | | | | | | | | | |
| Medical History/ Demographics | | | | | | | | | | | | |
| Randomization | | | | | | | | | | | | |
| Training on Daily Allergy Symptom Diary | | | | | | | | | | | | |
| Training on Study Drug Administration | | | | | | | | | | | | |
| Treatment: | | | | - | | - | | | | | | |
| Blinded Study Drug SC Q2W Administration ^{1,} | Х | Х | Х | Х | Х | Х | | | | | | |
| Subject Study Drug Injection Log ¹ | Х | Х | Х | Х | Х | Х | | | | | | |
| AR101 Daily Administration ² | Х | X | Х | X | X | Х | | | | | | |
| Daily subject AR101 Dosing Diary ² | X | X | X | X | X | X | | | | | | |
| AR101 Dispensation/Account ³ | Х | X | Х | X | X | Х | | | | | | |
| Epinephrine Autoinjector Training | | | | | | | | | | | | |
| Con Meds/Procedures | Х | Х | Х | X | Х | X | | | | | | |
| Efficacy ⁴ : | | | | | | | | | | | | |
| DBPCFC ⁵ | | | | | | | | | | | | |
| Peanut Skin Prick Test (SPT) ⁶ | | | | | | | | | | | | |
| Peanut SPT titrated ⁶ | | | | | | | | | | | | |
| EASI for AD, ACQ-5 asthma | Х | X | Х | Х | Х | Х | | | | | | |
| Daily Allergy Symptom Diary ⁷ | Х | X | Х | Х | Х | Х | | | | | | |
| FAQL Questionnaire | | | | | | | | | | | | |
| Safety ⁴ : | | | | | | | | | | | | |

CONFIDENTIAL

Page 69 of 86

| Study Procedure | | | Double-Blind T | reatment Period | | |
|--|------|------|------------------------------------|-----------------|------|------|
| | | S | Study Drug Conco AR101 Up-Dosin | | t | |
| Visit (V) | V15a | V15b | V15c | V15d | V15e | V15f |
| Week (W) ¹⁴ | W28 | W30 | W32 | W34 | W36 | W38 |
| Day (D) ¹⁴ | 197 | 211 | 225 | 239 | 253 | 267 |
| Visit Window (d) | ±2d | ±2d | ±2d | ±2d | ±2d | ±2d |
| Weight | Х | X | Х | Х | Х | Х |
| Height | | | | | | |
| Vital Signs ⁸ | Х | Х | Х | Х | Х | Х |
| Physical Examination | | | | | | |
| Spirometry/Peak Flow ^{9, 9a} | Х | X | Х | Х | Х | Х |
| Adverse Events | Х | X | Х | Х | Х | Х |
| Laboratory Testing ⁴ : | | | • | | | |
| HIV ab, HBsAg, HBcAb, Hep C Ab | | | | | | |
| Hematology, Chemistry | Х | | | | Х | |
| FeNO Test ^{9,9a} | Х | | Х | | Х | |
| Urinalysis | Х | | | Х | Х | Х |
| Pregnancy Test (WOCBP only) | U | U | U | U | U | U |
| Total IgE | Х | | | | Х | |
| sIgE, sIgG4, sIgG Against Peanut Extract and Peanut Allergen Components | Х | | | | Х | |
| Future Biomedical Research Sample (Optional) | Х | | | | Х | |
| Optional blood samples for additional exploratory research (eg, TruCulture, Basophil sensitivity, PBMC, allergen-specific T-cell profiling) ¹⁰ | | | | | | |
| DNA sample (Optional) ¹¹ | | | | | | |
| Functional dupilumab PK sample | | Х | | Х | | Х |
| Anti-dupilumab antibody sample | | | | | | |

Abbreviations: S, serum; U, urine; FAQL, Food Allergy Quality of Life; FeNO, fractional exhaled nitric oxide; WOCBP, women of child bearing potential; PBMC, peripheral blood mononuclear cell; PK, pharmacokinetic

| Study Procedure | | | | enance P | | | Fol Study | Vithdra | Period d AR101 wal | Unschedul ed Visit (if applicable) | ET Visit (if applicable) | |
|---|---------------------------|-------------|-------------|--------------|--------------|--------------|----------------------------------|---------------|--------------------------|--|--------------------------------|---|
| Visit (V) | V16 | V17 | V18 | V19 | V20 | V21 | V22 | V23 | V24 | V25 EOS | | |
| Week (W) ¹³ | W28 - 40 | V16+ 4wk | V16+ 8wk | V16+ 12wk | V16+ 16wk | V16+ 20wk | W52 - 64, Vtar16 + 24wk | V16+ 28 wk | V16+ 32wk | W64 – 76, V16 + 36wk | | |
| Visit Window (d) | -7/+30 d ¹⁴ | ±3d | ±3d | ±3d | ±3d | ±3d | -7/+30 d ¹⁴ | ±3d | ±3d | -7/+30 d ¹⁴ | | |
| Treatment: | | | | | | | | | | | | |
| Blinded Study Drug Q2W SC Administration | Х | X | X | X | Х | Х | | | | | X 15 | |
| Subject Study Drug Injection Log ¹ | Х | Х | Х | Х | Х | Х | | | | | | |
| AR101 Daily Administration ² | Х | X | Х | Х | Х | Х | | | | | | |
| Daily Subject AR101 Dosing Diary ² | Х | X | X | Х | X | X | Х | | | | | |
| AR101 Dispensation/Account ³ | Х | Х | Х | Х | Х | Х | Х | | | | | Х |
| Concomitant medications/Procedures | Х | X | X | Х | X | X | Х | Х | Х | Х | Х | Х |
| Efficacy: ⁴ | | | | | | | | | | | | |
| DBPCFC ^{5, 14} | Х | | | | | | Х | | | Х | | |
| Peanut SPT titrated ⁶ | Х | | | | | | Х | | | Х | | Х |
| EASI for AD, ACQ-5 for asthma | Х | X | Х | Х | Х | Х | Х | X | X | Х | | Х |
| Daily Allergy Symptom Diary ⁷ | Х | Х | X | Х | X | X | Х | | | | Х | Х |
| FAQL Questionnaire | Х | | | | | | Х | | | Х | | |
| Safety: ⁴ | | | | | | | | | | | | |
| Weight | Х | Х | Х | Х | Х | Х | Х | Х | Х | Х | Х | Х |
| Vital Signs ⁸ | Х | X | X | Х | X | X | Х | X | Х | Х | Х | Х |
| Physical Examination | Х | | | | | | Х | | | Х | | Х |
| Spirometry/Peak Flow ^{9,9a} | Х | | | X | | | Х | | | Х | | Х |
| Adverse Events | Х | Х | Х | X | Х | Х | Х | Х | Х | Х | Х | Х |
| PEESS Questionnaire ¹⁰ | | | | | | | | | | | Х | Х |
| Laboratory Testing: 4 | | | | | | | | | | | | |
| HIV ab, HBsAg, HBcAb, Hep C Ab | | | | | | | | | | | | |
| Hematology, Chemistry | X | | | X | | | X | | | X | | Х |
| FeNO Test ^{9, 9a} | Х | | | Х | | | Х | | | Х | | Х |

Table 3: Schedule of Events – Maintenance Period and Follow-Up Period

| Urinalysis | Х | | | Х | | | Х | | Х | Х |
|-----------------------------|---|---|---|---|---|---|---|--|---|---|
| Pregnancy Test (WOCBP only) | U | U | U | U | U | U | U | | S | U |

| Study Procedure | Maintenance Period | | | | | | Post-Treatment Follow-up Period | | | Unschedul ed Visit (if | ET Visit (if | |
|---|---------------------------|-------------|-------------|--------------|--------------|--------------|------------------------------------|-------------------|--------------|-----------------------------------|-----------------|-------------|
| | | | | | | | | Study | | d AR101 | applicable) | applicable) |
| Visit (V) | V16 | V17 | V18 | V19 | V20 | V21 | V22 | V23 | V24 | V25 | | |
| Week (W) ¹³ | W28 - 40 | V16+ 4wk | V16+ 8wk | V16+ 12wk | V16+ 16wk | V16+ 20wk | W52 - 64, V16+ 24wk | V16 + 28 wk | V16+ 32wk | EOS W64 – 76, V16 + 36wk | | |
| Visit Window (d) | -7/+30 d ¹⁴ | ±3d | ±3d | ±3d | ±3d | ±3d | -7/+30 d ¹⁴ | ±3d | ±3d | -7/+30 d ¹⁴ | | |
| Total IgE | Х | | | Х | | | Х | | | Х | | Х |
| sIgE, sIgG4, sIgG Against Peanut Extract and Peanut Allergen Components | Х | | | Х | | | Х | | | Х | | Х |
| Future Biomedical Research sample (Optional) | Х | | | Х | | | Х | | | Х | | Х |
| Optional blood samples for additional exploratory research (eg, TruCulture, Basophil sensitivity, PBMC) ¹¹ | Х | | | | | | Х | | | Х | | Х |
| PK/Drug Concentration and ADA Samples: ⁴ | | | | | | | | | | | | |
| Functional dupilumab PK sample | Х | Х | Х | Х | Х | | Х | | | Х | Х | Х |
| Anti-dupilumab antibody sample | Х | | | Х | | | Х | | | Х | Х | Х |

Abbreviations: EOS = End of study; ET = Early termination; WOCBP = Women of child bearing potential

Footnotes for the Schedule of Events Table 2

1. The subject/legal guardian will administer SC study drug as scheduled on dosing days. Subject/legal guardian will complete an injection log (e-diary) to document compliance with injection of study drug. On days when both dupilumab/placebo study drug and AR101 are administered, the study drug will be administered at least 8 hours apart from the AR101 and at least 24 hours after the start of in-clinic dosing.

Regeneron Pharmaceuticals, Inc. Statistical Analysis Plan

- 2. The subject/legal guardian will administer AR101 during the days in which no in-clinic visit is scheduled. Subject/legal guardian will complete a dosing diary to document compliance with AR101. On the day following in-clinic up-dosing, the site is to make telephone contact to inquire if any AEs occurred and report appropriately.
- 3. Starting at visit 4 (week 4), AR101 will be dispensed at the site to the subject/caregiver for the doses that will be administered before the next clinic visit.
- 4. Assessments will be performed before the administration of study drug.
- 5. Subject will be observed for a minimum of 2 hours after the final administered dose and discharged only when deemed clinically stable by a study doctor. On the day following a food challenge, the site must make telephone contact to inquire if the subject experienced any AEs and report appropriately. Before each challenge, the subject will have a physical assessment performed by a trained physician's assistant, registered nurse, nurse practitioner, and/or physician of the study team who is blinded to the testing material. Eczema Area and Severity Index and ACQ only needed be completed once during day 1 of the food challenge.
- 6. Subjects should not take anti-histamines for at least 5 days prior to the SPT.
- 7. Site should confirm subject compliance at each clinic visit.
- 8. During DBPCFC, vital signs will be collected every 15 to 30 minutes. During maintenance phase for in-clinic office visits, the post-dose observation may be shortened to 30 minutes.
- 9. Spirometry will be performed in-clinic on the same day whenever FeNO measurement is scheduled; however, spirometry will also be performed at other visits when FeNO is not collected. FeNO should be done prior to spirometry. If the DBPCFC is scheduled on the day of the visit, then both FeNO measurement and spirometry will be performed twice before the subject goes home: once before DBPCFC, once after DBPCFC.
 - a. During the COVID-19 pandemic, measurements of FeNO no longer need to be completed while on study (although FeNO is still required at screening). Additionally, if spirometry cannot be completed after enrollment, peak flow may be performed instead at the discretion of the investigator (although spirometry is still required at screening).
- 10. On the day of the DBPCFCs, blood draws for optional exploratory research-will be performed before the DBPCFC is performed. For the day 1 exploratory research sample, the last DBPCFC must be \geq 15 days before to ensure washout of peanut allergen.
- 11. One optional DNA sample for the genomics analyses (buccal swab) can be collected on day 1 (visit 2) or any other visit.
- 12. Must complete all visit 1 assessments and confirm eligibility before visit 1a.
- 13. Visit 1a must occur at least 15 days before visit 2 to allow a 2-week washout after the peanut screening DBPCFC.

CONFIDENTIAL

Page 73 of 86

VV-RIM-00131540-1.0 Approved - 02 Nov 2020 GMT-5:00

Regeneron Pharmaceuticals, Inc. Statistical Analysis Plan

- 14. The time points listed in this table correspond with the bi-weekly up-dosing schedule. These time points may no longer be accurate following adjustments to the planned up-dosing period. As of Amendment 3, the up-dosing period has been permitted to be extended to accommodate COVID-19 restrictions of in-clinic visits, as well as dose reductions and re-escalation, if necessary. This extension permits a maximum up-dosing period of 40 weeks, while 28 weeks is ideal (consisting of 4 weeks pretreatment, 22 to 34 weeks of up-dosing, and at least 2 weeks at the maximum dose.)
- 15. Study drug administration at unscheduled and/or optional visits 15a-f is to be documented in the unscheduled visits folder.

Footnotes for the Schedule of Events Table 3

- 1. The subject/legal guardian will administer SC study drug as scheduled on dosing days. Subject/ legal guardian will complete an injection log (e-diary) to document compliance with injection of study drug. On days when both dupilumab/placebo study drug and AR101 are administered, the study drug will be administered at least 8 hours apart from the AR101 and at least 24 hours after the start of in-clinic dosing. Both days of the post up-dosing DBPCFC at visit 16 should be completed before starting the visit 16 SC study drug as part of the maintenance phase.
- 2. The subject/legal guardian will administer AR101 during the days in which no clinic visit is scheduled. Subject/caregiver will complete a dosing diary to document compliance with AR101.
- 3. Starting at visit 4 (week 4), AR101 that is dispensed at the site to the subject/legal guardian will be accounted for.
- 4. Assessments will be performed before the administration of study drug.
- 5. The food challenges will be performed on different days (1-day placebo [oat] protein, 1-day peanut protein, with order determined at random) at least 24 hours, but not more than 7 days, apart and not within 24 hours of a dose of SC study drug. Subject will be observed for a minimum of 2 hours after the final administered dose and discharged only when deemed clinically stable by a study physician. On the day following a food challenge, the site must make a telephone contact to inquire if the subject experienced any AEs and report appropriately. Before each challenge, the subject will have a physical assessment performed by a trained physician's assistant, registered nurse, nurse practitioner, and/or physician of the study team who is blinded to the testing material. Eczema Area and Severity Index and ACQ only needed be completed once during day 1 of the food challenge.
- 6. Subjects should not take anti-histamines for at least 5 days prior to the SPT.
- 7. Site should confirm subject compliance at each clinic visit.
- 8. During DBPCFC, vital signs will be collected every 15 to 30 minutes.

Regeneron Pharmaceuticals, Inc. Statistical Analysis Plan

- 9. Spirometry will be performed in-clinic on the same day whenever FeNO measurement is scheduled; however, spirometry will also be performed at other visits when FeNO is not collected. FeNO should be done prior to spirometry. If the DBPCFC is scheduled on the day of the visit, then both FeNO measurement and spirometry will be performed twice before the subject goes home: once before DBPCFC, once after DBPCFC.
 - a. During the COVID-19 pandemic, measurements of FeNO no longer need to be completed while on study (although FeNO is still required at screening). Additionally, if spirometry cannot be completed after enrollment, peak flow may be performed instead at the discretion of the investigator (although spirometry is still required at screening).
- 10. Only for patients who discontinue for GI AEs. If applicable, after week 64 PEESS will be collected by phone.
- 11. On the day of the DBPCFCs, blood draws for optional exploratory research-will be performed before the DBPCFC is performed.
- 12. Clinic visits are monthly. However, SC study drug administration is Q2W and dosing diaries for AR101 and allergic symptoms are done daily.
- 13. The time points listed in this table correspond with the bi-weekly up-dosing schedule. These time points may no longer be accurate following adjustments to the planned up-dosing period. As of Amendment 3, the up-dosing period has been permitted to be extended to accommodate COVID-19 restrictions of in-clinic visits, as well as dose reductions and re-escalation, if necessary. This extension permits a maximum up-dosing period of 40 weeks, while 28 weeks is ideal (consisting of 4 weeks pretreatment, 22 to 34 weeks of up-dosing, and at least 2 weeks at the maximum dose.)
- 14. If subjects are not able to go into the clinic for the DBPCFC within the target time frame, the DBPCFC can be started up to 7 days before and 30 days after the target date for visit 22 and/or visit 25.
- 15. Study drug administration at unscheduled and/or optional visits 15a-f is to be documented in the unscheduled visits folder.

| Parameter | Treatment Emergent PCSV | Comments |
|---|--|---|
| Clinical Chemistry | | |
| Alanine Aminotransferas e | >3 and \leq 5 ULN and baseline \leq 3 ULN >5 and \leq 10 ULN and baseline \leq 5 ULN | Enzyme activity must be expressed in ULN, not in IU/L. Concept paper on DILI – FDA draft Guidance |
| (ALT) | >10 and \leq 20 ULN and baseline \leq 10 ULN >20 ULN and baseline \leq 20 ULN | Oct 2007. Each category is calculated independently. |
| Aspartate Aminotransferas | >3 and \leq 5 ULN and baseline \leq 3 ULN >5 and \leq 10 ULN and baseline \leq 5 ULN | Enzyme activity must be expressed in ULN, not in IU/L. |
| e (AST) | >10 and \leq 20 ULN and baseline \leq 10 ULN | Concept paper on DILI – FDA draft Guidance Oct 2007. |
| | >20 ULN and baseline ≤ 20 ULN | Each category is calculated independently. |
| Alkaline Phosphatase (ALP) | >1.5 ULN and baseline \leq 1.5 ULN | Enzyme activity must be expressed in ULN, not in IU/L. |
| (ALF) | | Concept paper on DILI – FDA draft Guidance Oct 2007. |
| Bilirubin (BILI) | >1.3 ULN and baseline \leq 1.3 ULN | Must be expressed in ULN, not in μ mol/L or mg/L. |
| | | Based on normal range: $<1 \text{ mg/dL}$, CF = mg x $1.7 = \mu \text{mol}$ |
| | | Concept paper on DILI – FDA draft Guidance Oct 2007. |
| | | Based on normal ranges: <6 mg/dL (Term 0-1 day), <8 mg/dL (Term 1-2 days), <12 mg/dL (Term 3-5 days), <1 mg/dL (Term >5 days) |
| Conjugated Bilirubin | (Direct Bilirubin >35% Total Bilirubin and Total Bilirubin ≥1.3 ULN) and (Direct Bilirubin ≤35% Total Bilirubin or Total | Conjugated bilirubin will be measured when the total Bilirubin is above the ULN |
| | Bilirubin ≤ 1.3 ULN) at baseline | Based on normal range: 0 to 0.4 mg/dL |
| (ALT or AST) and Bilirubin (BILI) | ((ALT > 3 ULN or AST >3 ULN)) and BILI >2 ULN) and baseline ((ALT ≤3 ULN or AST ≤3 ULN) or BILI ≤2 ULN) | Concept paper on DILI – FDA draft Guidance Oct 2007. |
| Creatine Kinase | >5 ULN and baseline ≤5 ULN | FDA Feb 2005. |
| (CK) | >10 ULN and baseline ≤ 10 ULN | Am J Cardiol April 2006. |
| | | Categories are cumulative. |

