8.3.2.2. Reasons for Temporary Discontinuation of SC Study Drug

Study drug dosing will be temporarily discontinued in the event of:

• Clinically important laboratory abnormalities such as:

Regeneron Pharmaceuticals, Inc.

CONFIDENTIAL

Page 63 of 118

- Neutrophil count $<1.5 \times 10^3/\mu L$ but $>0.5 \times 10^3/\mu L$
- ALT or AST $3 \times ULN$ but $\leq 5 \times ULN$
- Platelet count $\leq 100 \times 10^{3}/\mu L$ but $> 50 \times 10^{3}/\mu L$
- Creatinine phosphokinase (CPK) >2.5 x ULN
- Serum creatinine >1.5 x ULN
- Eosinophils >5000/ μ L
- Severe laboratory abnormalities (as noted in Section 8.3.2.1) where a causal relationship to dupilumab can be reasonably excluded (ie, an alternative cause is evident). In these cases, study treatment will be discontinued while the clinical circumstances are being assessed but it may be resumed when the laboratory parameters normalize sufficiently. A decision to resume treatment will be made jointly by the investigator and medical monitor
- Other intercurrent illnesses or major surgery
- An infection that requires parenteral treatment with antibiotic, antifungal, antiviral, antiparasitic, or antiprotozoal agents, or requires oral treatment with such agents for longer than 2 weeks

After the condition leading to suspension of dosing normalizes sufficiently, study treatment may resume at the discretion of the principal investigator in consultation with the medical monitor. A decision to discontinue study drug and/or to reinstitute study treatment should be discussed with the medical monitor. Note that dosing may NOT be resumed if subject met conditions for permanently discontinuing study drug described in Section 8.3. The investigator may suspend study treatment at any time, even without consultation with the medical monitor, if the urgency of the situation requires immediate action and if this is determined to be in the subject's best interest. However, the medical monitor should be contacted as soon as possible in any case of study drug discontinuation. Resumption of study treatment after temporary discontinuation should always be discussed with the medical monitor.

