10.4.5. Abnormal Laboratory or Vital Signs Results

Abnormal laboratory or vital signs will be graded according to the FDA September 2007. The criteria for determining whether an abnormal objective test finding should be reported as an AE include:

- the test result is associated with accompanying symptoms, and/or
- the test result requires additional diagnostic testing or medical/surgical intervention, and/or
- the test result leads to a change in dosing (outside of protocol-stipulated dose adjustments), discontinuation from the study, significant additional concomitant drug treatment, or other therapy

Contact the medical monitor in the event the investigator feels that an abnormal test finding should be reported as an AE, although it does not meet any of the above criteria.

Repeating an abnormal test, in the absence of any of the above conditions, does not constitute an AE. Any abnormal test result that is determined to be an error does not require reporting as an AE.

Please refer to FDA Guidance for Industry, Toxicity Grading Scale for Healthy Adult and Adolescent Volunteers Enrolled in Preventive Vaccine Clinical Trials for reporting severity of laboratory abnormalities:

(https://www.fda.gov/downloads/BiologicsBloodVaccines/GuidanceComplianceRegulatoryInfor mation/Guidances/Vaccines/ucm091977.pdf)

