10.3. Criteria for Potentially Clinically Significant Values (PCSV)

| Creatinine (CREAT) | >=30% increase from individual subject baseline >=60% increase from individual subject baseline | Benichou C., 1994. 2 independent criteria |
|--|--|--|
| Urate (URATE) Hyperuricemia Hypouricemia | >=30% increase from individual subject baseline >=60% increase from individual subject baseline | Harrison- Principles of internal Medicine 17th Ed., 2008. Two independent criteria |
| Urea Nitrogen (UREAN) | >=30% increase from individual subject baseline >=60% increase from individual subject baseline | |
| Chloride (CL) Hypochloremia Hyperchloremia | <80 mmol/L and baseline \ge 80 mmol/L >115 mmol/L and baseline \le 115 mmol/L | Two independent criteria |
| Sodium (SODIUM) Hyponatremia Hypernatremia | <129 mmol/L and baseline ≥129 mmol/L >150 mmol/L and baseline ≤ 150 mmol/L | Two independent criteria |
| Potassium (K) Hypokalemia Hyperkalemia | <3.5 mmol/L and baseline \ge 3.5 mmol/L >5.0 mmol/L and baseline \le 5.0 mmol/L | FDA Feb 2005. Two independent criteria |
| Cholesterol (Cholesterol) | >6.20 mmol/L and \leq 6.20 mmol/L at baseline | |
| Triglycerides (TRIG) | > 5.64 mmol/L and ≤ 5.64 mmol/L at baseline | Threshold for therapeutic intervention with pharmacotherapy in children. (Expert Panel on Integrated Guidelines for Cardiovascular Health and Risk Reduction in Children and Adolescents; 2011). CF = g x 1.14 = mmol |
| Glucose (GLUC) Hypoglycaemia Hyperglycaemia | ≤ 2.7 mmol/L ≥10 mmol/L | |
| Albumin (ALB) | <25 g/L and ≥ 25 g/L at baseline | |
| Calcium (CA) | <2 mmol/L and baseline ≥2 mmol/L >2.9 mmol/L and baseline ≤2.9 mmol/L | |

| LDL Cholesterol (LDL) | >4.91 mmol/Land ≤4.91 mmol/L at baseline | Threshold for therapeutic intervention with pharmacotherapy in children (Expert Panel on Integrated Guidelines for Cardiovascular Health and Risk Reduction in Children and Adolescents; 2011). |
|-----------------------------------|---|---|
| Hematology | | |
| Leukocytes (WBC) | <4.0 Giga/L and ≥4.0 Giga/L at baseline >13.5 Giga/L and ≤13.5 Giga/L at baseline | |
| Lymphocytes (LYM) | <0.6 Giga/L and ≥0.6 Giga/L at baseline >6.0 Giga/L and ≤6.0 Giga/L at baseline | |
| Neutrophils (NEUT) | <1.2 Giga/L and ≥1.2 Giga/L at baseline >ULN and baseline ≤ ULN | |
| Monocytes (MONO) | >1.2 Giga/L and \leq 1.2 Giga/L at baseline | |
| Basophils (BASO) | >0.2 Giga/L | |

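### CK above 2.5 and up to 5 × ULN, and neutrophils from 1.2 to below 1.5 Giga/L, pause study drug but meet no CK or low-neutrophil PCSV row; separately, the combined liver row mis-negates its baseline condition

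*SAP*

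**What the plan says.** Protocol 8.3.2.2 opens with "Study drug dosing will be temporarily discontinued in the event of" and then lists "Clinically important laboratory abnormalities such as" several named limits. Among them are "Creatinine phosphokinase (CPK) >2.5 x ULN" and a neutrophil count below 1.5 but above 0.5 × 10³/µL.

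SAP 10.3 sets the thresholds for potentially clinically significant values (PCSV). The first CK category is "Creatine Kinase | >5 ULN and baseline ≤5 ULN"; the next starts above 10 × ULN. The one low-neutrophil category is "<1.2 Giga/L and ≥1.2 Giga/L at baseline". The combined liver row flags ALT or AST above 3 × ULN together with bilirubin above 2 × ULN, on condition that at "baseline ((ALT ≤3 ULN or AST ≤3 ULN) or BILI ≤2 ULN" held.

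SAP 5.7.3 commits to by-visit descriptive statistics, to the number and percentage of subjects with a treatment-emergent PCSV, and to a listing with abnormal flags. The PCSV count is given twice: for all SAF subjects, and for those who did not meet the criterion at baseline. Shift tables are optional.

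**The concern.** The protocol treats these two limits as important enough to interrupt SC study drug, but the table that counts abnormal results by arm begins further out. A child paused for a CK of 4 × ULN or a neutrophil count of 1.3 Giga/L meets no row for that test.

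Pauses have consequences in this design. Missing more than two consecutive SC doses is a permanent stop (Protocol 6.1.2.3 and 8.3.2.1), and permanently stopping dupilumab also stops AR101 (Protocol 8.3.2). How many children in each arm cross the pause limits is therefore useful safety information, and no committed table gives it.

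The liver row raises a different issue. A baseline condition that is not the exact opposite of the flag lets a pre-existing abnormality be counted as new.

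**Working it through.** No sample-size or error-rate figure is involved. The check sets the cut-offs side by side and works through the logic of the liver row. Units agree, since 10³/µL equals Giga/L. The SAP's CK row and the protocol's CPK are the same test; SAP 4.6.3 lists it as creatine phosphokinase.

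**1. Pause limits against the first PCSV category**

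| Test | Protocol 8.3.2.2 pause limit | SAP 10.3 first category | Pauses drug, meets no row for that test |
|---|---|---|---|
| CK | > 2.5 × ULN | > 5 × ULN, baseline ≤ 5 | > 2.5 to 5 × ULN |
| Neutrophils, low | < 1.5 and > 0.5 | < 1.2, baseline ≥ 1.2 | 1.2 to < 1.5 Giga/L |
| ALT, AST | > 3 to 5 × ULN | > 3 to 5 × ULN, baseline ≤ 3 | none |
| Platelets | ≤ 100 and > 50 | < 100, baseline ≥ 100 | exactly 100 |

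The protocol text lacks an inequality sign before 3 in the ALT/AST line; it is read here as above 3. The transaminase and platelet rows track the pause list almost exactly, so CK and neutrophils stand out. More extreme values of both (CK above 5 × ULN; neutrophils below 1.2) pause drug and are counted, given a baseline inside the PCSV limit.

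**2. Whether another committed table fills the two bands**

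- Adverse events: a dosing change makes a laboratory value an AE when "the test result leads to a change in dosing (outside of protocol-stipulated dose adjustments), discontinuation from the study" applies (Protocol 10.4.5). The words in parentheses may exclude a pause that the protocol itself requires.
- AE tables: SAP 5.7.1 tabulates TEAEs leading to permanent discontinuation. Interruption of drug appears only as a field in the AE listings.
- Exposure: SAP 5.5.2 calculates duration regardless of temporary interruption. The number of doses is summarised, but not why any were missed.
- Compliance: SAP 5.5.1 splits only at 80%.

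None of these gives a by-arm count of subjects who crossed the two limits.

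**3. Liver row**

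Let A be ALT > 3 × ULN, B be AST > 3 × ULN and C be bilirubin > 2 × ULN.

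- Flag: (A or B) and C.
- Its exact opposite: (not A and not B) or not C.
- SAP baseline condition: (not A or not B) or not C.

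The last two differ only when exactly one enzyme is raised and C is true. Example at baseline: ALT 4, AST 2, bilirubin 2.5 × ULN.

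- Flag: (4 > 3 or 2 > 3) and 2.5 > 2 is true, so the criterion is already met.
- SAP condition: (4 ≤ 3 or 2 ≤ 3) or 2.5 ≤ 2 is true, so the subject passes as not meeting it.
- Correct condition: (4 ≤ 3 and 2 ≤ 3) or 2.5 ≤ 2 is false, so the subject is excluded.

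The conjugated bilirubin row just above negates its own two-part condition properly, apart from the boundary at exactly 1.3 × ULN. That suggests the liver wording is a slip.

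**The case against.** The strongest reply is that no stated rule is broken. Protocol 11.4.4.2 leaves the PCSV criteria to the SAP, a dosing threshold and a tabulation threshold serve different purposes, and the CK row cites its own sources. This stands: the two documents do not contradict each other, and the added rows are an improvement to reporting.

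A reader might infer that values which interrupt dosing go uncounted in general. The documents do not support that. The gap is confined to two bands. Within them, by-visit statistics and listings include every value, optional shift tables may, and some low-neutrophil subjects may meet the WBC row (below 4.0 Giga/L).

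A reader might also infer that such values can never be adverse events. The criteria in Protocol 10.4.5 are joined by and/or, so symptoms, further diagnostic testing or other therapy still qualify, and the investigator can raise other findings with the medical monitor. Whether a temporary discontinuation counts as a dose adjustment is itself unsettled: Protocol 8.3.1 and 8.3.2 treat modification and discontinuation separately.

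Finally, a reader might conclude that laboratory safety is understated overall, or try to put a percentage on the missed values. Neither document gives a CK or neutrophil distribution, so any percentage would come from the assumed one. The liver slip works the other way, as an over-count.

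On the liver row, the reply is that SAP 5.7.3 also counts PCSVs among subjects who did not meet the criterion at baseline, and SAP 5.7 defines treatment-emergent as developed or worsened. The subgroup count does exclude the affected subjects, but the all-SAF count still uses the row as written.

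**Conclusion.** The point holds in a limited form. CK above 2.5 and up to 5 × ULN, and neutrophils from 1.2 to below 1.5 Giga/L, pause SC study drug yet meet no CK or low-neutrophil PCSV row, and no other by-arm count is committed to. This follows from the stated cut-offs alone. The number of subjects involved cannot be computed from the documents. No efficacy conclusion is affected.

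The liver row is wrong as written. The effect should be rare, since it needs a subject with one raised enzyme and raised bilirubin at baseline who meets the criterion again on treatment. It is an over-count, confined to the all-SAF summary.

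Nothing here bears on which clinical limit is appropriate.

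**What to change.** In SAP 10.3, keep the existing rows and add two categories at the protocol's stated pause limits, tabulated by arm and study period like the others:

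- CK > 2.5 × ULN and baseline ≤ 2.5 × ULN. The CK categories are already cumulative, so this slots in.
- Neutrophils < 1.5 Giga/L and baseline ≥ 1.5 Giga/L.

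These count subjects who cross a limit, not subjects whose drug was actually paused; the table footnote should say so.

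In the combined liver row, change the baseline condition to `(ALT ≤3 ULN and AST ≤3 ULN) or BILI ≤2 ULN`.

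The cost is two table rows and one word, on data already collected. The downside is a few more flagged values in the safety tables. No dosing rule changes.
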